**Problem Statement and Specific Aims:**

According to the National Council on Potassium in Clinical Practice, potassium depletion is one of the most common electrolyte abnormalities found in the clinical setting (Cohn, Kowey, Whelton, & Prisant, 2000). Hypokalemia has been found to affect between 20-37% of hospitalized patients depending on disease process (Crop, Hoorn, Lindemans, & Zietse, 2007; Hemstreet, Stolpman, Badesch, May & McCollum, 2008; Widodo, Setiawan, Chen, Nainggolan, & Santoso, 2006). In addition, epidemiologic research has found that hypokalemia not only can result from an underlying disease but is frequently acquired in the hospital due to its high association with gastrointestinal losses and use of diuretics (Crop et al., 2007). Therefore, replacement of potassium becomes a common practice carried out by Medical/Surgical nurses caring for patients in acute hospitals. Although oral potassium replacement is an option, patients often require rapid replacement or are unable to be replaced orally. Once intravenous (IV) potassium is initiated, Medical/Surgical nurses are faced with patients experiencing chemical/infusion phlebitis and pain at the catheter insertion site regardless of using slow infusion rates due to the acidic pH of the solution. This results in Medical/Surgical nurses seeking evidence-based options to reduce these further complications. Currently, the use of lidocaine with IV potassium chloride has been found to reduce pain during infusion (Lim, Khoo, & Tweed, 1992; Morril & Katz, 1988; Pucino et al., 1988); however lidocaine has also been linked to chemical phlebitis (Bassan & Sheikh-Hamad, 1983) and does not assist with preventing the complications from infusing acidic solutions. Therefore, this study is interested in evaluating the use of sodium bicarbonate additive as a neutralizing agent to potassium chloride infusion.

The purpose of this study is to examine the impact 4% sodium bicarbonate additive during intravenous potassium chloride replacement for adult patients in three Medical/Surgical units. Using a randomized controlled blinded experimental study design, patients who are 21 years or older and alert, awake, and oriented at time of enrollment and have been ordered intravenous potassium chloride replacement will be recruited from three Medical/Surgical units during the first 24-48 hours of their admission.

The specific aim of the study is:

Aim 1: To compare patient outcomes (phlebitis, pain at peripheral IV insertion site, frequency of changing IV access, and time for administration) between the experimental (4% sodium bicarbonate additive during peripheral intravenous potassium chloride replacement therapy ) and control (standard of practice of no 4% sodium bicarbonate additive during peripheral intravenous potassium chloride replacement therapy) groups.

Aim 2: To compare number and type of nursing interventions done during peripheral IV potassium replacement therapy between the experimental (4% sodium bicarbonate additive during intravenous potassium chloride replacement) and control (standard of practice of no 4% sodium bicarbonate additive during peripheral intravenous potassium chloride replacement therapy) groups.

Aim 3: To compare attrition rates and reasons between the experimental (4% sodium bicarbonate additive during peripheral intravenous potassium chloride replacement therapy) and control (standard of practice of no 4% sodium bicarbonate additive during peripheral intravenous potassium chloride replacement therapy) groups.

**Significance:**

Hypokalemia, or the low concentration of potassium (below 3.5 mmol/l), is a condition that can result in serious adverse effects including disturbances in cardiac conduction along with muscle, kidney,

gastrointestinal tract, genitourinary tract, respiratory, and endocrine dysfunction (Asmar, Mohandas, & Wingo, 2012; Hemstreet, et al., 2008). Hypokalemia is typically a result of chronic medical conditions such as reduced intake of potassium, chronic diuretic therapy, diarrhea, short bowel syndrome, vomiting and burns. Although potassium can be replaced orally, IV potassium chloride is utilized in patients that need rapid replacement, are showing clinical signs of low potassium, or patients who are unable to orally ingest the replacement. Potassium should always be diluted and slowly administered to reduce the likelihood of pain from inflammation of the vein or phlebitis. (Pharmacology for the Prehospital Professional, 2011). Yet, even at slow rates of 10 mEq/h phlebitis and pain have been reported in 60% of patients (Stephens et al., 1976).

Peripheral venous cannulation (PVC) is a common procedure carried out in hospital to allow rapid and accurate administration of medication (Endacott et al., 2009). In replacing Potassium intravenously, nurses need to have intravenous access. In WKBH 3 South/3 North/4 South Medical-Surgical Telemetry units, nurses often receive orders for Potassium replacement through Intravenous route. The majority of these patients have peripheral intravenous access. The intravenous access is often started in the Emergency Department and continued once the patient is admitted. The peripheral intravenous site is being assessed per protocol for phlebitis once per shift and as needed.

Once the Physician orders the Potassium replacement intravenously, the Pharmacist prepares the medication. The nurse then, starts the infusion via the peripheral intravenous access. Nurses receive complaints of burning sensation or pain from patients as soon as the infusion is started. The nurse then would try to get an order for Neut (4 % sodium bicarbonate additive solution) to be added to the Potassium Chloride solution with the goal to minimize pain during infusion. Neut (4% sodium bicarbonate additive solution) is a neutralizing additive solution, a sterile non-pyrogenic solution of sodium bicarbonate in water for injection. It is administered by the intravenous route only after addition as a neutralizing agent to an acidic large volume parenteral solution. It is indicated for use as an additive to raise the pH of acid solutions administered intravenously to reduce the incidence of chemical phlebitis and patient discomfort due to vein irritation at or near the site of infusion. (APP Pharmaceuticals, 2008). Previous studies have concluded that one of the causes of infusion phlebitis was the pH of the solution (Lewis and Hecker, 1985; Kuwahara, et al 1998). A study conducted by Fujita et al 2000, confirmed that with the use of 7% Sodium Bicarbonate, moderate phlebitis was only experienced by 6% of the patients. Although cardiovascular abnormalities are rare when KCl is administered at an infusion rate of 10mEq/hour, phlebitis and pain reportedly occur in 60% of patients (Stephens et al 1976)).

The mechanism by which KCl causes pain and phlebitis upon I.V. administration is not known. A study by Morrill and Katz, 1988 provided evidence that Lidocaine in small doses is effective in reducing KCl-induced pain but no literatures have been found on the use of 4% Sodium Bicarbonate to reduce pain or phlebitis during intravenous Potassium replacement. This study will test the effects of 4% Sodium Bicarbonate additive during intravenous potassium chloride replacement. This study will also look at efficacy of 4% Sodium Bicarbonate in reduction and prevention of pain and phlebitis on patients receiving intravenous Potassium Chloride replacement.

#### **Methods:**

Staff Education: will include, but not be limited to: (1) an introduction to the study; (2) how potential participants will be screened (i.e. only patients that have been ordered peripheral intravenous potassium chloride replacement therapy as part of their care which is regardless of research); (3) how participants will be identified via sticker on chart; (4) how the intervention will be rolled out in collaboration with pharmacy and the medical staff; (5) how data collection will occur; and (6) who to contact if there are any questions about the study.

Recruitment (3 means):

- (1) The resource nurse will be provided a screening tool (please see attached screening flyer) to assess for potential participants on admission. The resource nurse will inform the principal investigator and/or designated key personnel either by phone or email that a potential participant

has been admitted. No identifying information will be provided. The principal investigator or designated key personnel will then talk with the resource nurse while on the unit in order to determine the potential participant's location on the unit and the direct patient care nurse assigned to her or him. The principal investigator or designated key personnel will then attempt to enroll the potential participant after: (a) the direct patient care nurse initiates contact with the potential participant (please see script); and (b) potential participant has agreed to meet with the principal investigator or designated key personnel.

- (2) The principal investigator will meet with the resource nurse or patient care supervisor (PCS) on 3 South/3 North/4 South to determine if any patients meet the inclusion criteria (please see attached screening flyer). If the principal investigator identifies a potential participant she will attempt to enroll the potential participant after: (a) the direct patient care nurse initiates contact with the potential participant (please see script); and (b) potential participant has agreed to meet with the principal investigator.
- (3) The designated key personnel will go to 3 South/3 North/4 South on a daily bases Monday through Friday and meet with the resource nurse or patient care supervisor (PCS) to see whether potential participants are on the unit, and ask for their room numbers and staff nurse assigned to them. The designated key personnel will then attempt to enroll the potential participant after: (a) the direct patient care nurse initiates contact with the potential participant (please see script); and (b) potential participant has agreed to meet with the designed key personnel.

#### Enrollment Process:

- (1) The study will be explained, consent and HIPAA; in either English or Spanish (which will be determined by the participant's personal choice), will be obtained (please see attached consent) after the principal investigator or designated key personnel has answered all questions. The potential participant will be provided with about 10 minutes of individual time to review the consent. Each participant will be provided a copy of their signed consent (please see attached).
- (2) Once enrolled the principal investigator or designated key personnel will: (a) contact the pharmacy to inform them that a new participant has been enrolled in the research study; (b) place a sticker on the chart of the participant (study number and enrollment date); and (c) place the participant (medical recorder number and study number provided by pharmacy) into the enrollment log. The pharmacy research team member will then randomize the participant into either the experimental group (4% sodium bicarbonate additive during peripheral intravenous potassium chloride replacement therapy) or the control group (standard of practice of no 4% sodium bicarbonate additive during peripheral intravenous potassium chloride replacement therapy) based on a randomization table. The randomization table will be generated by the statistician research team member after IRB approval is obtained by use of the statistical package nQuery. The pharmacy research team member will label the potassium replacement IV bags with a sticker to identify them as study participants. This will include the standard of practice of labeling the IV bags as potassium replacement and also a label stating "neut study participant" but without the designated grouping in order to maintain blinding. In order to maintain integrity of data and reduce bias the participant and direct patient care nurse will not be informed of randomization results. The pharmacy research team member will maintain a record of randomization that will be provided to the principal investigator.
  - a. Participants enrolled in the control group will receive standard of practice which is intravenous potassium replacement without the 4% sodium bicarbonate additive at the rate ordered by the ordering physician or ARNP for peripheral intravenous potassium chloride replacement therapy which will be part of the care of the patient regardless of research, and based on the WKBH policy of potassium chloride infusion of no more than 100ml/hr. Pharmacist prepares, as standard of practice, each bag of 100 ml normal saline (NS) with 10mEq potassium chloride.

- b. Participants enrolled in the experimental group (4% sodium bicarbonate additive during peripheral intravenous potassium chloride replacement therapy) will receive the additive after pharmacy and/or the designated key personnel ([name]) coordinates the ordering of 4% sodium bicarbonate additive during peripheral intravenous potassium chloride replacement therapy. Pharmacist prepares, when ordered as standard of practice, each bag of 100 ml NS with 10mEq Potassium Chloride and 5 ml of 4% sodium bicarbonate additive, therefore, this practice will be used for the experimental group. The rate of peripheral intravenous potassium chloride replacement therapy will be ordered by the ordering physician or ARNP, for IV potassium chloride replacement therapy which will be part of the care of the patient regardless of research, and based on the WKBH policy of potassium chloride infusion of no more than 100ml/hr.

[figure not shown]
Data Collection:

- (1) Demographics (please see attached) will be collected by the principal investigator or designated key personnel after enrollment of patient.
- (2) peripheral intravenous potassium chloride replacement therapy (please see attached) data collection form: assessment of peripheral IV insertion site for phlebitis, using the VIP tool, and pain, using the Likert 11 point scale will be collected at baseline (prior to any peripheral intravenous potassium chloride replacement therapy), at 15 minutes after infusion started, every hour until peripheral intravenous potassium chloride replacement therapy is complete, and then at completion of replacement.

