## **Other Pertinent Information:**

*Standard of Practice for Potassium chloride replacement therapy:* The Physician or ARNP evaluates the Potassium level of the patient and orders potassium replacement therapy for potassium level of 3.5 or below. The amount of replacement of potassium intravenously is determined by the patient's physician or ARNP based on patient's condition and potassium level as standard of practice and the order is provided to the direct patient care nurses and pharmacy. Patients with peripheral IV access may be ordered to receive intravenous potassium replacement therapy of 10 mEq/100 ml Normal Saline bag, ordered as one or multiple doses depending on the potassium level and patient's condition. The peripheral intravenous site is being assessed per protocol for phlebitis once per shift and as needed. During potassium chloride intravenous replacement direct patient care nurses can initiate nursing interventions including but not limited to: changing IV site, slowing rate of infusion, and requesting from the patient's physician or ARNP an order for 4% sodium bicarbonate additive solution.

*Study Procedures covered:* Those participants in experimental group who will receive up to 4 doses of 4% sodium bicarbonate will not be charged for those experimental doses. The Academy of Medical-Surgical Nurses (AMSN) is sponsoring this study and the cost of 4% sodium bicarbonate to Pharmacy will be covered by AMSN.

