### *Limitations*

This study has some limitations. Firstly, the sample will include patients in a Medical/Surgical units admitted for various reasons which can result in varying intravenous drug therapy. For this reason participants will be randomized and only those that have been on the unit for 24-48 hours will be approached for enrollment. Secondly, the direct patient care nurses will be assessing phlebitis and pain at IV insertion site which can reduce fidelity of data collection. Therefore, a reliable and valid tool will be used along with initial education and additional education at six months will be provided by the research team.

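### The additive order is described for the experimental arm only, with no stated masking of the order, so it can reveal the arm to the nurse who scores phlebitis

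*Combined protocol and SAP*

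**What the plan says.** The opening section calls the trial randomized, controlled and blinded. Enrollment Process (2) names who is blinded: "the participant and direct patient care nurse will not be informed of randomization results". The concrete measure given there is the bag label, which marks the bag as a study bag "but without the designated grouping in order to maintain blinding".

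The two arms then differ in how the bag is obtained:

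- **Control, (2)a:** participants receive "intravenous potassium replacement without the 4% sodium bicarbonate additive at the rate ordered by the ordering physician or ARNP". No order relating to the additive is mentioned.
- **Experimental, (2)b:** pharmacy and/or designated key personnel "coordinates the ordering of 4% sodium bicarbonate additive during peripheral intravenous potassium chloride replacement therapy". The wording for how this bag is made up is "when ordered as standard of practice, each bag of 100 ml NS with 10mEq Potassium Chloride and 5 ml of 4% sodium bicarbonate".

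Two sections describe usual practice. Significance says that a nurse whose patient complains of burning or pain will "try to get an order for Neut (4 % sodium bicarbonate additive solution) to be added to the Potassium Chloride solution". Other Pertinent Information says of potassium replacement that "the order is provided to the direct patient care nurses and pharmacy", and it lists requesting an additive order among the interventions open to the nurse.

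Limitations states that "the direct patient care nurses will be assessing phlebitis and pain at IV insertion site". Data Collection (2) has the same nurses return the form that records site changes, slowed rates and additive requests. It defines attrition by requests for the additive or for no additive. After such a request, or an adverse event, the pharmacist reveals the group.

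**The concern.** The bag is masked, but nothing is said about masking the order behind it. If the order or the medication record shows the additive for one arm and nothing for the other, a nurse who checks the order before hanging the bag learns the allocation at the start, outside the planned unblinding procedure.

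That nurse is also the outcome assessor. VIP scoring of early signs is a judgement, and so is the choice to change a site, slow the rate or ask for the additive. Attrition under Aim 3 is defined by what the nurse requests, and Data Collection (2) ties the collection of interventions and attrition to the nurse being blinded. A nurse who can see that the additive is already running has little reason to request it, so counts could differ between arms through knowledge alone. Assessor bias of this kind cannot be repaired in the analysis.

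**Working it through.** The plan gives no figure on this point to reproduce. The main check sets the text side by side; a hypothetical calculation follows.

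**Does the text leave an arm-specific cue?**

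1. Does the ordering step differ by arm? Yes. (2)b describes coordinating an order for the additive; (2)a describes nothing corresponding.
2. Does the additive normally carry its own order? Yes, by inference from Significance and Other Pertinent Information, where the nurse asks for it on top of the existing potassium order. (2)b does not itself say that the order is separate.
3. Do nurses see orders? Other Pertinent Information says so for the potassium order. Extending this to the additive order is an inference.
4. Is the order masked? The text describes the bag label and states that the nurse is not told the result. It mentions no common order, no dummy order for controls, and no suppression in the chart or medication record.
5. Would seeing the order be planned unblinding? No. The group is to be revealed only after a request about the additive or an adverse event.

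So an arm-specific cue exists, and nothing described keeps it from the nurse. Whether the nurse would in fact see it is not stated.

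**Which outcomes are exposed?**

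- VIP phlebitis: directly, since the nurse scores it.
- Site changes, slowed rates and additive requests (Aim 2, and IV changes in Aim 1): directly, since the nurse initiates them.
- Attrition (Aim 3): directly, but not necessarily in one direction, because requests for no additive count as well as requests for it.
- Pain: less directly, since the patient gives the 0–10 rating and the nurse collects it.

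**Hypothetical size for phlebitis**

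Inputs from the Participants section: phlebitis 0.15 without the additive, and 100 per group. Assumptions that are not in the documents: no true effect, and under-scoring of cases throughout the additive arm by a fraction f.

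Scored rates are p1 = 0.15 and p2 = 0.15 × (1 − f). The odds ratio is [p2/(1 − p2)] / [p1/(1 − p1)].

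P(reject) = Φ[(d − 1.96·s0)/s1] + Φ[(−d − 1.96·s0)/s1], where d = p1 − p2, s0 = √[2·p̄(1 − p̄)/100] with p̄ = (p1 + p2)/2, and s1 = √[p1(1 − p1)/100 + p2(1 − p2)/100].

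| f | p2 | OR | s0 | s1 | P(reject) |
|---|---|---|---|---|---|
| 0 | 0.150 | 1.00 | 0.0505 | 0.0505 | 0.050 |
| 1/5 | 0.120 | 0.77 | 0.0483 | 0.0483 | 0.095 |
| 1/3 | 0.100 | 0.63 | 0.0468 | 0.0466 | 0.187 |
| 1/2 | 0.075 | 0.46 | 0.0447 | 0.0444 | 0.388 |

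For f = 1/3: (0.05 − 1.96 × 0.0468)/0.0466 ≈ −0.89, giving 0.186. The other tail adds 0.001, for a total of 0.187. An exact binomial calculation gives 0.096, 0.189 and 0.397 for the three non-zero fractions.

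**The case against.** The strongest reply is that the leak is inferred. The sentence about orders reaching nurses concerns the potassium order, and no section says where the additive order is recorded or who sees it. The trial also departs from usual practice: pharmacy or key personnel arrange the additive, not the nurse, which may well serve the blind. The unblinding procedure makes sense only if the nurse does not already know the bag content, so the intent to blind is clear. A figure directly after (2)b and the attached forms are not available here and might show the order flow. All of this stands, and it limits the point to what the order *can* do.

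It does not remove the point. (2)b adopts the standard-practice preparation on an order and says nothing about what is displayed. Intent to blind is not a mechanism, and the one concrete mechanism covers only the bag.

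Two stronger readings are tempting. A reader might infer that nurses will be unblinded and that the trial cannot be called blinded; the documents do not establish visibility, so this does not follow. A reader might also infer that all three aims are biased toward the additive; pain is patient-rated and attrition counts requests in both directions, so a uniform direction is not supported.

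It is also fair to object that the under-scoring fractions are invented and applied to the whole arm; if only some nurses saw the order, the effect would be smaller. Finally, the extra 5 ml in the experimental bag might seem a second cue. Nothing indicates that a nurse would notice it, and matching it would alter the control preparation, which is defined as standard practice. No change is asked for there.

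**Conclusion.** The point holds as a gap in the masking procedure. As written, an additive order is arranged for one arm only and nothing described hides it from the nurse who assesses and acts on the outcomes. The conclusion rests on two inferences from usual practice: that the additive is ordered in its own right, and that its order could reach the nurse as the potassium order does. If the order is already kept out of view, the gap is one of wording.

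The size cannot be estimated from the documents. The false-positive rates of about 10%, 19% and 39% only show what under-scoring by one fifth, one third or one half would do; they do not predict this trial. This is a cheap improvement, worth making because the safeguard costs little and the bias could not be undone afterwards.

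**What to change.** In Enrollment Process (2), replace the experimental-only additive order with one study order used for every participant, worded along the lines of: potassium chloride replacement as ordered, with or without study additive, per pharmacy randomization table. State that it displays identically in the chart and medication record in both arms, that pharmacy alone holds the actual content, and that the content is released under the unblinding procedure already in Data Collection (2). If the additive order is already hidden from the direct care nurses, a sentence saying how would close the gap.

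The cost is one order entry agreed with pharmacy and a protocol wording change. Pharmacy already randomizes, labels the bags, keeps the allocation record and unblinds on need. No dose, rate or clinical rule changes. The small downside is that the chart does not show the additive until unblinding. The documents do not say whether the hospital's ordering system allows such an entry, so this should be confirmed first.
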